5.1.3.4. Relevant medical and surgical history

Medical and surgical history other than for the studied disease will be presented in a listing with system organ class (SOC) and preferred term (PT) according to Medical Dictionary for Regulatory Activities (MedDRA).

Listing will include onset date and grade, if applicable.

5.2. Treatments of patients

Treatment of patients will be described on the Safety Analysis Set.

5.2.1. Extent of exposure and treatment compliance

Ivosidenib in combination with nivolumab and ipilimumab will be administered every 21 days for the first four cycles and every 28 days for cycle 5 and beyond until the end of treatment for each patient.

The following variables are derived using non-zero doses of the IMPs:

- Cycles of exposure: number of cycles where patient received at least one dose
- Treatment duration (months): (last dose date - first dose date + 1) / 30.4375
- Planned cumulative dose (mg): sum of the planned doses administered for each cycle
 - Ivosidenib: planned dose level (mg) * x days
 - Nivolumab and ipilimumab: planned total dose (mg)
- Actual cumulative dose (mg): sum of the actual doses administered for each cycle
 - Ivosidenib: (tablets dispensed - tablets returned) * actual dose (mg)
 - Nivolumab and ipilimumab: actual total dose (mg)
- Planned Dose Intensity (PDI):
 - Ivosidenib: schedule dose level (mg/day)
 - Nivolumab and ipilimumab (mg/cycle): planned cumulative dose (mg) / number of planned cycles
- Actual Dose Intensity (ADI):
 - Ivosidenib (mg/day): actual cumulative dose (mg) / treatment duration (days)
 - Nivolumab and ipilimumab (mg/cycle): actual cumulative dose (mg) / cycle of exposure (cycles)
- Relative Dose Intensity (RDI) (%):
 - Ivosidenib: $100 \times \text{ADI (mg/day)} / \text{PDI (mg/day)}$
 - Nivolumab and ipilimumab: $100 \times \text{ADI (mg/cycle)} / \text{PDI (mg/cycle)}$

These exposure variables will be presented in listings for each drug. Cycles of exposure and treatment duration will be presented also for the overall treatment (any drug).

Treatment compliance will be presented in listings using the number of doses administered, the number of dose interruptions, number of dose delays, number of dose missed and number of dose reductions for each of the three drugs. Reasons for these actions will be included.

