6.1. IMPs Administered

Product Description and Dosage Form	Concentration	Primary Packaging	Secondary Packaging
Ivosidenib / tablet	Tablets of 250 mg	One pillbox = 60 tablets of 250 mg	One box containing one pillbox of 60 tablets
Nivolumab / solution for injection	CC1 mg/mL	One vial = CCI mL CC1 mg/mL	One box containing one vial
Ipilimumab / solution for injection	CC1 mg/mL	One vial = CCI mL vial at CC1 mg/mL	One box containing one vial

It is recommended that each dose should be taken with or without food. Subjects taking ivosidenib with food should be advised to avoid grapefruit or grapefruit products and avoid

consuming a high-fat meal (Please refer to examples of low-fat and high-fat meals in [Appendix 12](#)).

For treatment dose modifications due to toxicities, please refer to Section [8.12](#). All the IMP tracking is managed in RTSM in real time. The procedures to be followed by the Investigator or authorized person are detailed in the training video embedded in RSTM or user manual.

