3.2. Treatment groups

Treatment considered is ivosidenib in combination with nivolumab and ipilimumab.

For Safety Lead-in phase, 2 sequential dose groups will be considered:

- Ivosidenib 500 mg QD PO + nivolumab (3 mg/kg) + ipilimumab (1 mg/kg)
- Ivosidenib 250 mg QD PO + nivolumab (3 mg/kg) + ipilimumab (1 mg/kg)

The total number of dose levels tested will depend on the DLT observed. The RCD will be used for the Expansion phase.

In the unlikely event of a patient taking a different dose level from the planned dose level at Cycle 1 Day 1 (C1D1), the patient will be considered in the group corresponding to initial dose level taken at C1D1.

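### SAP 5.2.1 multiplies an ivosidenib tablet count by the dose instead of the 250 mg tablet strength, which doubles the computed exposure for time on 500 mg once daily

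*SAP*

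**What the plan says.** SAP 5.2.1 sets out the ivosidenib exposure variables as a chain.

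- Actual cumulative dose has a general definition, "Actual cumulative dose (mg): sum of the actual doses administered for each cycle", and an ivosidenib rule, "Ivosidenib: (tablets dispensed - tablets returned) * actual dose (mg").
- Planned cumulative dose is "Ivosidenib: planned dose level (mg) * x days".
- Planned dose intensity (PDI) is "Ivosidenib: schedule dose level (mg/day").
- ADI is "Ivosidenib (mg/day): actual cumulative dose (mg) / treatment duration (days").
- RDI is 100 times ADI divided by PDI.

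The SAP neither defines *actual dose* nor gives the tablet strength. The protocol does give it: section 6.1 has "One pillbox = 60 tablets of 250 mg", and the synopsis and section 4.2 also name only the 250 mg tablet. The first dose group in SAP 3.2 is "Ivosidenib 500 mg QD PO + nivolumab (3 mg/kg) + ipilimumab (1 mg/kg"). A second group at 250 mg was to follow if the DLT results called for it.

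**The concern.** A tablet count becomes milligrams when it is multiplied by milligrams per tablet. The SAP multiplies it by a dose. At 250 mg once daily the two coincide, because one tablet is one dose. At 500 mg once daily they do not: the two tablets that make up one dose are counted as two 500 mg doses. The PDI in the denominator is the scheduled daily dose and carries no such factor, so the error passes straight into RDI.

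With 7 patients and output mainly as listings, individual exposure values are what a reader will set beside each patient's adverse events. A fully compliant patient on 500 mg would appear to have taken twice the assigned dose. A patient who took half the tablets would appear fully dosed. Protocol 8.12.1 allows reduction from 500 to 250 mg, so the size of the error can also change within one patient.

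**Working it through.** The documents state no exposure or RDI figure, so there is nothing to reproduce first. The check applies the SAP's own formulas twice, changing only the multiplier.

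**Inputs**
- Tablet strength: 250 mg (Protocol 6.1, 4.2, synopsis).
- Dose levels: 500 mg once daily = 2 tablets a day; 250 mg once daily = 1 tablet a day (SAP 3.2 with the tablet strength).
- Cycle length: 21 days for Cycles 1 to 4, then 28 days (SAP 5.2.1).
- PDI: 500 mg/day in the 500 mg group (SAP 5.2.1).

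**Formulas**
- Tablets taken = dispensed − returned.
- Cumulative dose = tablets taken × multiplier. As worded, the multiplier is the dose; corrected, it is 250 mg.
- ADI = cumulative dose / days.
- RDI = 100 × ADI / PDI.

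**One 21-day cycle, 500 mg once daily, full compliance.** One bottle of 60 is dispensed and 18 tablets are returned, so 42 are taken. The planned dose is 500 × 21 = 10,500 mg.
- As worded: 42 × 500 = 21,000 mg.
- Corrected: 42 × 250 = 10,500 mg, which equals the plan.

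**Other cases**

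| Case | Tablets | Cumulative dose, as worded | RDI, as worded | Cumulative dose, corrected | RDI, corrected |
|---|---|---|---|---|---|
| 500 mg, 42 days, full compliance | 84 | 42,000 mg | 200% | 21,000 mg | 100% |
| 500 mg, 42 days, 75% of tablets | 63 | 31,500 mg | 150% | 15,750 mg | 75% |
| 500 mg, 42 days, half of tablets | 42 | 21,000 mg | 100% | 10,500 mg | 50% |
| 500 mg, one 28-day cycle, full compliance | 56 | 28,000 mg | 200% | 14,000 mg | 100% |
| 250 mg, 42 days, full compliance | 42 | 10,500 mg | 100% | 10,500 mg | 100% |

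The factor is exactly 2 at 500 mg, whatever the compliance or duration, and exactly 1 at 250 mg.

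**Dose reduced part-way** (illustration: 21 days at 500 mg, then 21 days at 250 mg, PDI held at 500 mg/day).
- As worded: 42 × 500 + 21 × 250 = 26,250 mg; 26,250 / 42 = 625 mg/day; RDI 125%.
- Corrected: 63 × 250 = 15,750 mg; 15,750 / 42 = 375 mg/day; RDI 75%.

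The ratio here is 26,250 / 15,750 = 1.67, so halving the output afterwards does not repair it.

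**Two further gaps in the chain**
- The ADI formula needs days, but SAP 5.2.1 defines treatment duration only in months (days / 30.4375).
- The SAP does not say whether PDI stays at the starting level after a reduction. In the illustration, a PDI that follows the reduction would be (21 × 500 + 21 × 250) / 42 = 375 mg/day. The corrected RDI would then be 100% rather than 75%.

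**The case against.** The strongest reply is that *actual dose* is undefined and could mean milligrams per tablet. Elsewhere in the same list the assigned dose is called a dose level, and this line does not use that term. Only a per-tablet strength gives milligrams when multiplied by a tablet count. Only one strength exists, and under Protocol 6.4 the diary records the strength of the tablets taken. A programmer who reads it that way gets the right answer.

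That reading is possible, but nothing in the SAP states it. The general definition directly above the line uses the same words for doses administered, the parallel planned line multiplies a daily dose by days, and Protocol 10.1.4 speaks of the dose received. The derivation is correct only if the programmer departs from how the surrounding text uses the word.

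The second reply is about reach, and it stands. Enrollment stopped at 7 patients, no hypothesis is tested, and these variables appear only in listings. No adverse event table or DLT listing is specified to use RDI. Section 5.2.1 separately lists doses administered, interruptions, delays, missed doses and reductions, so compliance can be checked another way. An RDI of 200% would also be conspicuous. The half-compliance case would not be, because it shows as 100%.

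**Conclusion.** Wrong as written; should be fixed. Followed as worded, the rule doubles ivosidenib cumulative dose, ADI and RDI for all time on 500 mg once daily, and is correct at 250 mg once daily. This rests on reading *actual dose* as the dose taken.

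A reader might infer more, in three ways that the documents do not support.

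- **That every patient on 500 mg will show an RDI of about 200%.** That figure needs full compliance with no interruption or reduction. The general result is a doubling of whatever the true value is while on 500 mg, and a smaller factor overall once the dose has been reduced.
- **That under-dosed patients would pass the 75% ivosidenib requirement for the DLT-Evaluable Set.** SAP 3.1 and Protocol 4.1.4.2 and 10.1.2 define that requirement directly, without reference to cumulative dose, ADI or RDI. Protocol 4.1.4.2 adds a judgement by the investigator and sponsor that the safety data suffice. No text connects the two.
- **That results have already been miscalculated.** The documents contain no program and no output.

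The first 6 patients were planned for 500 mg. The documents do not give the dose level of each of the 7 enrolled, so the number affected is not stated.

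**What to change.** In SAP 5.2.1:

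1. Replace the ivosidenib line under actual cumulative dose with: (tablets dispensed − tablets returned) × 250 mg (tablet strength), summed over cycles.
2. For ivosidenib ADI, state that treatment duration is in days: last dose date − first dose date + 1.
3. State that PDI remains the assigned starting dose level when the dose is later reduced. This agrees with SAP 3.2, which groups patients by the dose level taken at Cycle 1 Day 1.

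The first change removes the doubling. The second and third are needed for ADI and RDI to be fully specified, including after a reduction. The cost is three lines of SAP text and one derivation to program and check. No new data are needed, and no dose or clinical rule changes.

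### SAP 5.2.1 computes nivolumab and ipilimumab dose intensity per dosed cycle instead of over time, as protocol 10.1.4 requires, and SAP Section 7 does not declare the change

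*SAP*

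**What the plan says.** Protocol 10.1.4 (Exposure) defines dose intensity as actual dose received over actual duration. It defines RDI as that ratio relative to planned dose over planned duration, for each drug separately.

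SAP 5.2.1 sets these rules:

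- Antibody actual dose intensity (ADI): "Nivolumab and ipilimumab (mg/cycle): actual cumulative dose (mg) / cycle of exposure (cycles").
- Antibody planned dose intensity (PDI): "planned cumulative dose (mg) / number of planned cycles". RDI is 100 × ADI / PDI.
- "Cycles of exposure: number of cycles where patient received at least one dose". This is a count, defined apart from the date-based "Treatment duration (months): (last dose date - first dose date + 1) / 30.4375".
- Ivosidenib ADI does use time: "Ivosidenib (mg/day): actual cumulative dose (mg) / treatment duration (days").
- "These exposure variables will be presented in listings for each drug". The next sentence adds an any-drug version of cycles and duration as an extra display, so the count that enters antibody ADI is per drug.
- Compliance listings include the "number of dose delays, number of dose missed and number of dose reductions for each of the three drugs", with reasons.

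SAP Section 7, on changes to protocol-planned analyses, reports none.

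**The concern.** RDI should show how much of the planned combination was delivered over the planned time. Protocol 8.12.3 bars dose modification of nivolumab and ipilimumab, so their intensity falls mainly through delay or omission. Protocol 8.12.2 foresees delays of more than 8 weeks on the 3-weekly schedule and 10 weeks on the 4-weekly schedule. A per-cycle ratio does not register a delay: a late cycle still counts as one cycle.

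Two columns with the same label would then measure different things. Ivosidenib RDI falls with an interruption, while antibody RDI stays at 100% with a delay of the same length. The study report would also carry a definition other than the protocol's without saying so.

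**Working it through.** Neither document states a dose-intensity figure, so there is none to reproduce. The check compares the two definitions on the same dosing histories, which are illustrative.

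**Inputs.** Ipilimumab 1 mg/kg for 4 doses every 21 days; nivolumab 3 mg/kg for the same 4 doses, then 480 mg every 28 days (SAP 1.2). Ipilimumab is taken as 70 mg per dose; weight cancels.

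**Formulas.**
- SAP: RDI = 100 × (actual dose / dosed cycles) / (planned dose / planned cycles).
- Protocol: RDI = 100 × (actual dose / actual duration) / (planned dose / planned duration).

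Protocol 10.1.4 does not say where a duration ends, so two conventions are shown, each used on both sides: 4 × 21 = 84 planned days, or first to last dose plus one, 63 + 1 = 64 planned days.

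**1. Ipilimumab, all 4 doses given, total delay D.** The SAP gives (280/4)/(280/4) = 100% for any D. Over time the doses cancel, leaving planned over actual duration.

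| D (days) | SAP | 84-day convention | 64-day convention |
|---|---|---|---|
| 0 | 100% | 84/84 = 100% | 64/64 = 100% |
| 28 | 100% | 84/112 = 75.0% | 64/92 = 69.6% |
| 42 | 100% | 84/126 = 66.7% | 64/106 = 60.4% |
| 56 | 100% | 84/140 = 60.0% | 64/120 = 53.3% |

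For contrast, take ivosidenib under the SAP's own rule, with 84 dosed days at 500 mg and a 28-day interruption: (500 × 84/112)/500 = 75.0%.

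**2. Ipilimumab dose 3 omitted, dose 4 on time.** The omitted cycle leaves the dosed-cycle count, so ADI = 210/3 = 70 mg/cycle. PDI is 70 mg/cycle whether taken as 280/4 or 210/3, provided planned dose and planned cycles cover the same cycles. SAP RDI = 100%. Over time the durations are equal, so RDI = 210/280 = 75.0%.

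**3. Nivolumab across the switch to 480 mg.** The number of planned cycles is undefined. Take 4 weight-based doses and one 480 mg dose given.
- Matched to the 5 cycles dosed: planned equals actual, so RDI = 100% despite any delay.
- Counted by calendar, with a sixth cycle due but not yet given, at assumed weights:
  - 50 kg: (1080/5)/(1560/6) = 216/260 = 83.1%
  - 70 kg: (1320/5)/(1800/6) = 264/300 = 88.0%
  - 90 kg: (1560/5)/(2040/6) = 312/340 = 91.8%

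The delay acts here only by adding a 480 mg cycle to the planned average. The result varies with body weight and is not a measure of time.

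**4. Ivosidenib wording.** The SAP multiplies tablets used by the actual dose in mg. Tablets are 250 mg (protocol 6.1). At 500 mg once daily for 21 days, 42 tablets are used: 42 × 500 = 21,000 mg read literally, against 42 × 250 = 10,500 mg taken, which is double.

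**The case against.** The strongest reply is that little is hidden. SAP 5.2.1 already lists, per drug, doses administered, delays, missed doses with reasons, cycles of exposure and treatment duration. With 7 participants, a reader can see four ipilimumab doses spread over 106 days instead of 64. Protocol Section 10 calls itself a general outline, and mg per cycle is an understandable unit for a drug given once per cycle. All of this stands as a limit on impact. It does not remove the contradiction, because protocol 10.1.4 gives an explicit formula and the SAP replaces it silently.

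Three stronger conclusions might be inferred, and the documents do not support them.

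- **That no delay can ever lower antibody RDI.** For nivolumab this needs matched planned and dosed cycles. A calendar count, which the undefined term allows, does move the figure.
- **That the SAP's last-minus-first-plus-one duration is unusable for antibodies.** On-time ipilimumab gives 84/64 = 131.3% only if a 64-day actual duration is set against an 84-day planned one. With 64 days on both sides it gives 100%.
- **That it is open whether cycles are counted per drug or for any drug.** The any-drug count is presented as an addition to the per-drug listings, so the per-drug reading is settled.

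**Conclusion.** The antibody rule is wrong as written, and the point is minor. SAP 5.2.1 departs from protocol 10.1.4 and from its own treatment of ivosidenib, and Section 7 does not say so.

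For ipilimumab with all 4 doses given, planned and dosed cycles always match and the listed RDI is blind to delay. The overstatement at 42 to 56 days is about 33 to 40 percentage points on the 84-day convention, or 40 to 47 on the 64-day one. An omitted dose is overstated by 25 points when planned dose and planned cycles cover the same cycles. For nivolumab the size cannot be fixed until the number of planned cycles is defined.

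The dosing histories and nivolumab weights are assumptions. The documents do not show what delays the 7 participants had. RDI enters no decision, and DLT and AE results are unaffected.

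**What to change.** For each antibody, compute RDI as (actual cumulative dose / actual duration) / (planned cumulative dose / planned duration), as in protocol 10.1.4. State one duration convention and use it for both actual and planned. Take planned dose and planned duration over the same scheduled cycles, including any that were skipped.

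If the per-cycle formula is kept, declare it in Section 7, define the number of planned cycles, and do not present the result as the protocol's RDI. In that case also clarify "Planned cumulative dose (mg): sum of the planned doses administered for each cycle", which can mean all scheduled doses or only those in cycles dosed.

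For ivosidenib, multiply the tablet count by tablet strength (250 mg).

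The cost is a few lines of SAP text and a small programming change for 7 participants; exposure is already derived from recorded doses and dates. The downside is that antibody RDI will look less favourable where doses were delayed or omitted.

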5.2.2. Prior and concomitant medications

Prior medications other than for the studied disease are defined as non-study medications taken prior to or at the time of the first dose of IMPs.

Concomitant medications are defined as non-study medications taken at the time of or after the first dose of IMPs and prior to the last dose plus 35 days.

All non-study medications will be coded according to World Health Organization Drug Dictionary (WHODD).

Prior and concomitant medications will be presented in listing according to Anatomical Therapeutic Chemical (ATC) code into 4 levels (Pharmacological class, Pharmacological subclass, Therapeutic class, Preferred name).

All non-study medications will be listed, including indication, dose, frequency, route, start date and end date.

A listing of medical and surgical procedures coded according to MedDRA dictionary will also be provided.

5.2.3. Subsequent therapies

Subsequent therapies are defined as anti-cancer therapies that are started after the last dose of IMPs.

Subsequent anti-cancer therapies will be coded according to WHODD and presented in a listing by ATC code classification level 3 and preferred name.

5.3. Efficacy analyses

Tumor response is evaluated as per RECIST v1.1 (Eisenhauer, et al., 2009) in patients by the investigator.

Since the study stopped enrollment after enrolling 7 patients for the Safety Lead-in phase and did not proceed to the Expansion phase, only listings will be generated for efficacy analyses for the Safety Lead-in phase. The listings will be based on the Safety Analysis Set and will include response assessments and best overall response (BOR).

BOR will be based on all post-baseline disease assessments until the first documentation of progressive disease (PD) or end of treatment, and prior to the initiation of a subsequent anti-cancer therapy, whichever occurs first.

BOR may include the following categories: CR, PR, stable disease (SD), PD and non evaluable (NE). Definitions of the response categories are the following:

- CR: at least two CRs at least 4 weeks apart.
- PR: at least two PRs or better (PR followed by PR or PR followed by CR) at least 4 weeks apart, and not qualifying for a CR.
- SD: at least one SD assessment (or better) \geq 36 days after start of IMPs, and not qualifying for CR or PR.
- PD: documentation of PD after start of IMPs (and not qualifying for CR, PR, SD).
- NE: all other cases.

5.4. Safety analyses

All safety analyses will be performed in the Safety Analysis Set and summaries will contain only data collected during the on-treatment period, unless otherwise specified.

5.4.1. Adverse events

5.4.1.1. Dose Limiting Toxicity (Safety Lead-in phase)

DLT is defined for the DLT evaluation period (first 42 days of dosing (i.e., Cycles 1 and 2) of the Safety Lead-in phase) and it is described in protocol Section 4.1.4.2. Details of the observed DLTs will be presented in a listing based on the DLT-Evaluable Set and only for the Safety Lead-in phase.

5.4.1.2. Adverse Events

Definition:

- Treatment-Emergent Adverse Events (TEAEs) are defined as all adverse events:
 - which occur or worsen between the first IMP administration date of any drug (included) and the last IMP administration date of any drug + 30 days (included), or between the first IMP administration date of any drug (included) and the last nivolumab administration + 100 days (included) for IMAEs,
 - The seriousness and the relationship with the IMPs of the adverse event are based on investigator opinion.

Analysis:

Adverse events will be coded according to MedDRA dictionary, and their severity classified according to National Cancer Institute Common Terminology Criteria for Adverse Events (NCI CTCAE) v5.0.

Number of events, number and percentage of patients reporting at least one event will be presented in a summary table for TEAEs by SOC, PT and severity.

An overall summary with number and percentage of patients in the following categories will be presented:

- All TEAEs.
- Treatment-related (for any drug) TEAEs.
- Ivosidenib-related TEAEs.
- Nivolumab-related TEAEs.
- Ipilimumab-related TEAEs.
- Grade 3 or higher TEAEs.
- Grade 3 or higher treatment-related TEAEs.
- SAEs.
- Treatment-related SAEs.
- AESIs.
- TEAEs leading to treatment discontinuation of any study drug.
- TEAEs leading to dose reduction of ivosidenib.
- TEAEs leading to on-treatment deaths.

Listings will be provided for TEAEs, SAEs, TEAEs leading to treatment discontinuation of any study drug, and TEAEs leading to on-treatment death.

The date/time of onset, date/time of recovery, action taken with IMPs, seriousness criteria and outcome will also be included in listings.

